2. RESEARCH DESIGN AND METHODS

2.1 CLASSIFICATION AND METHODOLOGICAL DESIGNS

The iNO OHCA study is a phase II double blind (participants and investigator) placebo controlled randomized (1:1) clinical trial of iNO 20 ppm administered over 12h (with 1 h weaning off) beginning as soon as possible but within 4 h of return of spontaneous circulation (ROSC) after OHCA. Planned enrollment is 130 subjects over 24 months at UPMC Presbyterian (PUH) and Mercy (MER) with randomization stratified in blocks of 8. Recruitment will be performed under exception from informed consent (EFIC) to facilitate early enrollment and treatment. The study will have a safety monitor to assess any concerns during its conduct and a pre-specified safety analysis at the mid-point (after 1 year or 60 patients whichever occurs first). Subjects or their surrogate (as subjects will be enrolled when comatose) will be notified as soon as possible by a member of the research team of enrollment and can elect whether to permit blood banking for future genetic studies.

Duration of subject participation is 90 ± 3 d of ROSC. Most data will be collected within four days of ROSC, which includes the 12h of study drug administration and 1h weaning of study drug. After the initial four days have passed follow up will be done at hospital discharge (DC; which includes death), day 30, and day 90 after OHCA to evaluate outcomes.

Subjects will not be withdrawn from or prevented from receiving any known effective therapy for the purposes of participating in this research.

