2.2 DETAILED DESCRIPTION OF STUDY DESIGN

Study Visits and Procedures:

Timepoint	Task
Pre-Enrollment	Screening for inclusion and exclusion criteria
Before Administration of Study Drug, 0h	PCAS MD Baseline, Baseline lab data, ECHO and LSCI
During Study Drug Administration, 0h-13h	Vitals, Labs, ECHO, LSCI
Retrospective Baseline Data	Demographics, OHCA data, Clinical Lab data
Day 1 Post ROSC	VS, Labs, Clinical Lab data, PCAS MD Daily data, Interventions, Medications, SOFA
Day 2 Post ROSC	VS, Labs, Clinical Lab data, PCAS MD Daily data, Interventions, Medications, SOFA
Day 3 Post ROSC	VS, Labs, Clinical Lab data, PCAS MD Daily data, Interventions, Medications, SOFA
Discharge	Survival, CPC, mRS, CPC-E, Barthel ADL, NYHA Class, Location
30d Follow Up	Survival, CPC, mRS, CPC-E, Barthel ADL, NYHA Class, Location
90d Follow Up	Survival, CPC, mRS, CPC-E, Barthel ADL, NYHA Class, Location

****Please note that the 0h ECHO and LSCI may be collected up to one hour after the administration of the study drug to avoid issues with timing of enrollment.**

The majority of data, including all clinical lab data, that is collected for this study will be gathered during a single hospitalization. All labs will be collected within 30 minutes of their assigned time.

Follow-up data that will be obtained will not require a subsequent visit, but rather just a phone call.

Most of the baseline data elements can be effectively gathered retrospectively and will not be needed prior to starting the study drug. A small number of data elements will indeed need to be captured before study drug is administered but these can be done fairly rapidly to preclude delays in therapy onset. The same is true for data elements in days 1-3 post-arrest (0-24 h after ROSC is considered day 1)

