***Methemoglobin to be collected at 6 hours only**

DAY 1-3 (0-72 h post-ROSC) DATA

During post-ROSC days 1-3, the following data elements will be collected by a physician coinvestigator/research assistant prospectively or by a research assistant retrospectively. Refer to chart for visual of when labs will be drawn.

- Plasma labs measured variably between 24 and 72 h (troponin, arterial blood gas, lactate, plasma nitrite level, neuron specific enolase, ascorbate, cardiolipin, plasma banking)
- Urine labs measured variably between 24 and 72 h (renal failure and nitrated fatty acid measurements)
- *Full Outline of UnResponsiveness (FOUR) Score (components below)
- Eyes
- Motor
- Brainstem
- Reflex
- *Glasgow Coma Score (GCS)
- Eyes
- Verbal
- Motor
- EEG interpretation
- Dominant background present
- Reactivity present
- Seizures present
- Seizure type
- Burst-suppression ratio
- Estimate of survival to hospital DC
- Median nerve SSEP
- Witnessed aspiration
- New suspected infection last 24h
- Infection type
- Sputum color
- Vent mode
- Set Vt
- Set PC
- PEEP
- FiO2 (Use % oxygen)
- Peak Pressure
- Plateau Pressure
- CXR last 24h read may be pneumonia
- Positive airway culture last 24h

- Vital Signs (VS) (highest and lowest for each)
- Time to follow commands (assigned once)
- SOFA (worst in prior 24h period; some components may be missing)
- Respiratory (when no PaO₂ is available for PaO₂:FiO₂ ratio, use SpO₂:FiO₂ ratio)
- Nervous (based on GCS below)
- Cardiovascular
- Liver
- Coagulation
- Renal
- Interventions
- Coronary angiography
- PCI
- ECMO
- CPR
- CABG
- Mechanical ventilation hours
- NIPPV hours
- 24h FiO₂ AUC
- Tracheostomy
- Medications (dichotomous for use not dose)
- Alteplase
- Anti-epileptic
- Midazolam infusion
- Intermittent Benzodiazapine
- Propofol infusion
- Intermittent Propofol
- Opiate infusion
- Intermittent opiate
- Neuromuscular blockade infusion
- Intermittent neuromuscular blockade
- Neurostimulants
- *Vasopressors
- *Inotropes
- Ketamine
- Steroids (hydrocortisone/methylprednisolone)
- Cumulative vasopressor index (CVI; worst in prior 24h period)
- *BUN (highest value in prior 24 h)
- *Creatinine (highest value in prior 24 h)
- Hb
- WBC
- platelets
- PT
- INR
- PTT
- Bilirubin
- AST

- ALT
- BNP
- SvO2 (%)
- venous PaO2
- venous PaCO2

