2.4 STUDY ENDPOINTS

Primary

Composite of in-hospital death, unfavorable discharge location, NYHA class III/IV heart failure at the time of discharge*

*In the setting of pre-existing heart failure or prior residence in an unfavorable location there must be at least a 1 class decrement (eg NYHA III -> IV)

Secondary

Functional

- Survival to hospital discharge, 30 and 90 days after initial OHCA
- Favorable cerebral performance category (CPC) defined as 1 or 2 at discharge, 30 and 90 days after initial OHCA
- Favorable modified Rankin score (mRS) defined as 0-3 at discharge, 30 and 90 days after initial OHCA
- Favorable discharge destination or location of residence (30 and 90 days after OHCA) defined as home or acute inpatient rehabilitation
- CPC-E at hospital discharge, 30 and 90 days after initial OHCA
- Barthel Index of Independence in Activities of Daily Living (ADL) at discharge, 30 and 90 days after OHCA

Neurologic

- Estimated likelihood of good neurologic outcome (0-100%) assessed by an experienced (>3y) member of the PCAS team blinded to treatment assignment on day 3-5 post-ROSC.
- Development of malignant EEG during hospitalization

- Time (in hours) to awakening from ROSC; defined as following commands (all values > 96h assigned 100)
- FOUR Motor + Brainstem scores on days 1-3 (requires 30 min off sedation; exclude endpoint if not medically permitted to pause sedation or paralysis)
- Presence or absence of upper and lower extremity somatosensory evoked potential N20 on comatose patients obtained any time after post-arrest day 1.
- Absolute value 24h after ROSC and change in value (24h vs 0h) of neuron specific enolase (NSE)
- EEG burst suppression ratio and change in suppression ratio
- EEG presence of dominant continuous background and reactivity to photic or tactile stimulation.

Cardiovascular

- Heart rate and mean arterial pressure (preferably off the arterial line) at 0-12 (hourly), 24h of study drug
- Persistent need for vasopressors in the first 24h after ROSC; defined as any use of norepinephrine, epinephrine, phenylephrine, dopamine or vasopressin for ≥ 3 h after study drug is initiated
- Persistent need of inotropes in the first 24h after ROSC; defined as any use of epinephrine, dobutamine, milrinone or isoproterenol for ≥ 3 h after study drug is initiated.
- ECHO measures (absolute values at end of therapy (12h) and change in 12h vs 0h):
 - tricuspid valve regurgitant velocity (TRV)

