3.2 INCLUSION CRITERIA

Inclusion criteria do not change any subgroups.

Intubated and comatose adult (>18 yo)

Out-of-hospital cardiac arrest (OHCA)

Cardiac arrest within an emergency department or outpatient medical center will be included.

OHCA includes EMS witnessed cardiac arrest.

ROSC within 40 min of CPR initiation

FOUR Brainstem score ≥ 2

Patient must have pupil OR corneal reflex before enrollment

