5. RECRUITMENT AND INFORMED CONSENT PROCEDURES

5.1 RECRUITMENT METHODS:

PCAS physicians are generally alerted to incoming resuscitated cardiac arrest patients either through a med call page (to accept the patient in transfer) or a page from emergency medical services stating the patient is en route to the emergency room (ER). PCAS physicians will review details of the patient's cardiac arrest to determine eligibility in consultation with a study coordinator. The ultimate designation of whether a patient is eligible will require a physical exam to determine neurologic function and hemodynamic stability upon ER presentation. If a patient is deemed eligible, they will be enrolled into the trial. We are requesting a waiver of informed consent to both review medical records to determine eligibility, and to enroll patients in the trial.

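### The day-1 FOUR window opens at ROSC, up to 4 h before study drug, and nothing bars a pre-drug exam from being used as the day-1 efficacy score

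*Combined protocol and SAP*

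**What the plan says.** The synopsis and section 2.4 (Neurologic) both give "FOUR Motor + Brainstem scores on days 1-3" as a secondary endpoint. The only condition attached is 30 minutes off sedation, and the endpoint is excluded where sedation or paralysis cannot medically be paused.

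The clock for these days is set in section 2.2: "0-24 h after ROSC is considered day 1". The collection list in the same section is headed "DAY 1-3 (0-72 h post-ROSC) DATA". FOUR appears there as a starred (essential) item, with no exam time and no rule for choosing among several exams. Items on that list may be collected "prospectively or by a research assistant retrospectively".

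Section 2.1 has study drug "beginning as soon as possible but within 4 h of return of spontaneous circulation (ROSC) after OHCA". Before that, section 3.2 requires a "FOUR Brainstem score" of at least 2 for entry, and section 5.1 says the eligibility decision "will require a physical exam to determine neurologic function and hemodynamic stability upon ER presentation". The baseline data list in section 2.2 contains neither FOUR nor GCS.

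**The concern.** An efficacy outcome should be measured after treatment has had a chance to act. Here the outcome window is tied to ROSC while treatment starts later, so the two clocks leave a stretch of day 1 that precedes study drug. The eligibility exam takes place in that stretch. If its score, or that of any other pre-drug exam, went into the day-1 field, a baseline value would be analysed as an outcome. Apart from chance, such a value is the same in both arms, so it can only weaken a true difference.

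FOUR is one of several neurologic secondary endpoints, but section 2.5.3 treats improvement in any secondary clinical outcome as preliminary evidence of efficacy that would lead to a larger trial. A diluted score could hide such a signal. There is also a missed gain: at least the Brainstem part of FOUR must be assessed before drug, yet no plan is stated to use it as a covariate. Section 2.5.2 provides covariate adjustment only for the composite endpoint, and only if confounders turn out unbalanced.

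**Working it through.** The plan gives no effect size, standard deviation or power for FOUR, so there is no figure to reproduce. The check is whether a pre-drug exam fits the definition of the day-1 score.

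**Timing**

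- Day-1 window: 0 to 24 h after ROSC (section 2.2).
- Study drug start: no later than 4 h after ROSC (section 2.1).
- Arrival: 1 to 3 h after ROSC for most patients at the larger site (section 2.3.3).
- Eligibility exam: after arrival and before drug, so for those patients between 1 h and 4 h after ROSC. That lies inside 0 to 24 h.

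On timing alone, the eligibility exam is a day-1 exam.

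**Rules that could exclude it**

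- A condition that the exam follow study drug: none for FOUR. By contrast, the vasopressor and inotrope endpoints in section 2.4 count use after study drug is started, and the ECHO measures are set at 12 h against 0 h.
- A rule for choosing among exams: none for FOUR. SOFA, on the same list, takes the worst value in the prior 24 h.
- Off-sedation condition: this applies to every days 1-3 exam, including an early one. It removes a sedated admission exam but not an unsedated one.
- Components: the endpoint needs Motor and Brainstem, whereas eligibility names Brainstem only. The eligibility exam would serve only if Motor was also scored.

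**How much of the window is pre-drug**

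Pre-drug share of the window = start time / 24. For starts at 1, 2, 3 and 4 h this is 1/24 = 4%, 2/24 = 8%, 3/24 = 13% and 4/24 = 17%.

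That counts time before arrival, when the study physician cannot examine the patient. For arrival at hour a and the latest permitted start, the share of the in-hospital window is (4 - a)/(24 - a). For a = 1 it is 3/23 = 13%, and for a = 3 it is 1/21 = 5%.

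These are shares of time. They equal shares of exams only if exam times are spread evenly, and no document says they are.

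**What dilution would do (illustration only)**

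Let f be the share of day-1 scores taken before drug, equal in both arms. The expected day-1 difference is multiplied by (1 - f). Take 65 per arm, a two-sided 0.05 test, and a true difference with 80% power at f = 0, which is (1.960 + 0.842) × √(2/65) = 0.49 SD. Power is then Φ(2.802 × (1 - f) - 1.960):

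- f = 5%: Φ(0.70) = 76%
- f = 10%: Φ(0.56) = 71%
- f = 13%: Φ(0.48) = 68%

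The 0.49 SD effect, the 65 evaluable subjects per arm and every value of f are assumptions. The number evaluable would be lower wherever sedation could not be paused.

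**The case against.** The strongest reply is that the protocol already separates baseline from day 1. The schedule in section 2.2 lists a baseline physician record before study drug, then the dosing period, then a daily physician record for day 1, and FOUR is collected with the daily items. Several of those items look back over the preceding 24 h, which suggests a record completed late in the day. Together with the off-sedation condition and the need for a Motor score, this makes a later exam the more natural reading. It also cannot be said that the eligibility FOUR goes unrecorded: the contents of the baseline physician record are not shown, and the screening questionnaire is cited as attached but is not in the text.

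All of this stands as evidence on likelihood. It does not close the gap, because the daily record still has no exam time and remains labelled by ROSC day. Retrospective collection does not imply that staff would pick a pre-drug value, but nothing tells them not to.

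A reader might go further and infer that the day-1 score is the eligibility exam, so that the day-1 effect is zero by construction. The documents do not support that, for the reasons above. A reader might also object to exams made while the gas is running. With 12 h of drug and a 1 h wean, gas ends 14 to 17 h after ROSC for starts at 1 to 4 h, so many day-1 exams could fall during treatment. Those exams can still show a treatment effect and are not a defect.

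**Conclusion.** The concern holds as a gap in the endpoint definition. The ROSC-based window admits a pre-drug value as the day-1 outcome, no rule excludes it, and no baseline FOUR is listed. The documents do not show that this would happen often.

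Any effect is dilution toward no difference, confined to the day-1 comparison and to a pooled days 1-3 comparison if one is made under the mixed models of section 2.5.2. Its size cannot be estimated from the documents, because they give neither exam times nor an expected effect on FOUR. The 5% to 13% range above describes time available at the latest permitted start for arrivals at 1 to 3 h; it is not a forecast of how many scores would be pre-drug. Day-2 and day-3 scores fall after drug start, and the primary composite is untouched. The change is worth making because it is nearly free and makes use of an assessment already required for entry.

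**What to change.** In section 2.4, the matching synopsis entry and the days 1-3 data list in section 2.2:

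- State that the day-1 FOUR must come from a qualifying exam (off sedation as already specified) after study drug start, and that a pre-drug exam may not fill the day-1 field.
- Record the date and time of the exam used.
- Keep days 2 and 3 on the existing post-ROSC clock. Moving them to 48 h and 72 h from drug start could put the day-3 exam at 72 + 4 = 76 h after ROSC, outside the stated 0-72 h window. Nor is there a need to wait until the gas has ended.
- Add the eligibility FOUR (Brainstem, and Motor where scored) to the baseline list as the 0 h value.

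In section 2.5.2, name that 0 h value as a covariate in the days 1-3 FOUR comparison.

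The cost is protocol wording, a time entry and one added CRF field for an assessment already made at entry. A few subjects may have no qualifying exam between drug start and the end of day 1; their day-1 score would be missing instead of filled with a pre-drug value.

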Study Aims:	
 1. Determine whether iNO (compared to placebo) provides clinical benefit when used within 4h of ROSC after OHCA. 2. Determine which mechanistic pathways are activated through use of iNO therapy and whether any of these are associated with outcome. 3. Determine whether iNO at 20 ppm provides a physiologic effect as determined by a significant reduction in tricuspid regurgitant velocity compared to placebo. 4. Determine whether RH measured by LSCI predicts subjects who will have a physiologic and/or clinical response to iNO.

	
5. Determine whether iNO reduces oxidant stress and mitochondrial injury after OHCA compared to placebo.
 
6. Measure plasma nitrite and S-nitrosothiol levels, as a surrogate of total plasma bioavailable NO, in all subjects.

Study Design:	Phase II double blind (participants and investigator) placebo controlled randomized (1:1) clinical trial of iNO 20 ppm administered over 12 hrs beginning as soon as possible but within 4 hrs of ROSC after OHCA.
Planned Sample Size:	130 subjects
Duration of Treatment:	12h
Major Inclusion Criteria:	
Intubated and comatose adult (>18 yo)
 
Out-of-hospital cardiac arrest (OHCA)
 
Cardiac arrest within an emergency department or outpatient medical center will be included.
 
OHCA includes EMS witnessed cardiac arrest
 
ROSC within 40 min of CPR initiation
 
FOUR Brainstem score ≥ 2
 
Patient must have pupil OR corneal reflex before enrollment

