The following data elements will be collected during the course of the study at the times indicated. Data elements marked with an asterisk indicate variables or outcomes essential for conduct of the study and analysis of efficacy and/or safety. These data elements should be obtained in all subjects with no missing data expected. In addition to these data elements, we are collecting a large amount of secondary data intended for use in mechanistic studies and hypothesis generation. In many cases, these data elements WILL NOT be able to be collected in all subjects. Such missing data will be handled as designated within an a priori statistical analysis plan but the presence of missing data will in no way impede our ability to meet the objectives of this phase 2 RCT.

BASELINE DATA

- *Date of OHCA
- *Time of OHCA (If not available we will use Time of ROSC after subtracting estimated no flow and CPR time based on transfer records/physician report)
- Witnessed
- Bystander CPR
- EMS Call Date
- EMS Call Time
- EMS Arrival Date
- EMS Arrival Time
- No flow time
- CPR (low flow) time
- Presenting rhythm
- *Date and Time of ROSC (If not available we will use ED admission date/time from referring hospital record. If unavailable, stat medevac call date/time minus 30 mins. If unavailable, time of arrival minus 15 min)
- PCAS ID
- *Last name
- *First name
- *Date of Birth
- *Medical record number
- Marital status
- Race/Ethnicity
- *Male Sex
- *Height
- *Weight
- Post-resuscitation chest pain

- Charlson Comorbidity
- Age Adjusted for Charlson Comorbidity Index (CCI)
- *New York Heart Association (NYHA) class pre-OHCA (if no surrogate is present and no medical records are found on the subject this will be assumed to be NYHA class I)
- Barthel ADL pre-OHCA
- Education level
- Private insurance
- Medicare
- Medicaid
- Employed
- Active smoker
- Smoker >20 pack-years
- Prior stroke
- Prior Coronary artery bypass grafting (CABG)
- Noninsulin-dependent diabetes mellitus (NIDDM2) type 2
- Insulin-dependent diabetes mellitus (IDDM2) type 2
- Diabetes mellitus (DM1) type 1
- Prior myocardial infarction (MI)
- Congestive Heart Failure (CHF)
- Chronic Obstructive Pulmonary Disease (COPD)
- Prior cardiac arrest
- Dementia
- Hyperlipidemia
- Hypertension
- Prior coronary stent
- Obstructive sleep apnea
- Pulmonary hypertension
- *Location pre-OHCA

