2.3.3. Dose Selection

A number of studies have reviewed the safety of iNO in adults primarily in the setting of acute respiratory distress syndrome (ARDS). A recent meta-analysis found improved oxygenation but also greater acute kidney injury (AKI) resulting from iNO use.²⁵ When this was examined by dose, AKI only resulted in those patients receiving higher cumulative doses of iNO (≥ 40 ppm for ≥ 48 h).²⁶ Our study will limit iNO to 20 ppm for 12h hence AKI is not expected though we will track BUN and creatinine on all subjects. A separate meta-analysis examining effects of iNO in

acute hypoxic respiratory failure in adults and children found no associated adverse events.²⁷ A study of iNO used in transport identified no adverse events associated with the drug.²⁸ Although iNO significantly increases methemoglobin (metHb) levels, the increase (0.3%) is clinically insignificant and not associated with toxicity²⁹ which is uncommon until levels of 20-30% (we will consider > 10% a significant and unexpected adverse event). The best predictor of significant metHb >4% (as < 0-3% is considered within normal range) is cumulative iNO dose of >2000 ppm * h.³⁰ In our study subjects will receive only 250 ppm * h. We will monitor methemoglobin as part of our study at 6h. Although iNO lowers pulmonary blood pressure it has not been linked to reduction in systemic arterial blood pressure. We will monitor blood pressure effects closely in our study given the inherent instability of cardiac arrest subjects.

Effects of iNO after cardiac arrest has been studied in 4 preclinical animal studies.⁸⁻¹¹ These published studies demonstrated benefit using iNO 40 ppm started within 2h of ROSC which is additive to therapeutic hypothermia⁸ as well as neuroprotection without temperature control.⁹ These animal models include mouse and pig models of asystole and ventricular fibrillation (VF). In addition iNO has been shown to protect in animal models of focal heart¹²⁻¹⁵ and brain¹⁶⁻¹⁹ injury. This is important since most of the mortality and morbidity after OHCA results from heart and brain injury.²⁰

Animal models of asphyxia²¹ and other focal brain ischemia reperfusion models demonstrate NO deficiency early in reperfusion lasting at least 6h and benefits from iNO.^{16,19}

Information from prior clinical trials of iNO are available by cross reference in the Mallinckrodt NDA 20-845 (letter authorizing cross reference is included with application).

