2.5.5 Handling Missing Data

Since our primary endpoint is ascertained at hospital discharge we expect no missing data though all analyses will be performed assuming a missing at random mechanism. No data imputation will be performed though standard sensitivity analyses, using standard missing data techniques may be used.

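### The FOUR Motor + Brainstem endpoint leaves out assessments when sedation or paralysis cannot be paused, a post-randomisation state that could differ by arm, and the missing-data plan does not address it

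*Combined protocol and SAP*

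**What the plan says.** Section 2.4 (Neurologic) and the Protocol Synopsis list FOUR Motor + Brainstem on days 1-3 as a secondary endpoint. The assessment needs 30 minutes off sedation, and the instruction is to "exclude endpoint if not medically permitted to pause sedation or paralysis".

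In section 2.2, the Day 1-3 data list puts an asterisk against "Full Outline of UnResponsiveness (FOUR) Score". The same section explains the asterisk: such elements are essential to the analysis, and "These data elements should be obtained in all subjects with no missing data expected". It allows for missing values only in the other, secondary elements.

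Section 2.5.5 says that "all analyses will be performed assuming a missing at random mechanism" and then "No data imputation will be performed though standard sensitivity analyses, using standard missing data techniques may be used". No sensitivity analysis is named. Section 2.5.2 provides mixed models for repeated assessments and tests everything two-sided at an unadjusted 0.05. Section 2.5.3 treats improvement in any secondary clinical outcome as preliminary evidence of efficacy.

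The documents give no expected exclusion rate for FOUR, no plan to report exclusions by arm, and no FOUR rule for subjects who die before an examination.

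**The concern.** The rule selects assessments by a clinical state that arises after treatment has been allocated. If patients who cannot be paused tend to be sicker, and if treatment changes who can be paused, the examined groups are no longer comparable in the way randomisation made them. A drug that only made more of the sicker patients examinable would look neurologically worse. One that made fewer examinable would look better. A missing-at-random analysis does not correct this when permission to pause depends on aspects of the patient's condition that the recorded scores do not capture.

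Exclusions are unlikely to be rare. Section 6.4.5 expects more than half of subjects to need more than 50% FiO2 and/or vasopressors in the first 24 h, and says that many will receive therapeutic hypothermia. FOUR is an early readout of brain injury in a trial of neuroprotection, so a distorted FOUR comparison could encourage or discourage the larger trial that section 2.5.3 has in view.

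**Working it through.** **The plan's own figure.** No power or exclusion figure is given for FOUR. The only design figure is for the primary composite (section 2.5.1): 60 per arm, a 23-point reduction, control rate 80-85%, power above 80%. A pooled two-sample test of proportions at two-sided 0.05 gives 78.1% at a control rate of 80% and 82.3% at 85%, so the figure is roughly reproduced. This point does not depend on it.

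**Timing.** Study drug begins "beginning as soon as possible but within 4 hrs of ROSC after OHCA" and runs for 12 h plus a 1 h wean, so it ends by about 4 + 12 + 1 = 17 h after ROSC. Day 1 is 0-24 h after ROSC (section 2.2). Days 2 and 3 are therefore examined after study drug has stopped.

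**Bias when there is no true effect.** From the plan: 65 randomised per arm, two-sided 0.05. Assumed, because the documents give no figures:
- a = share assessable on placebo, 0.60 to 0.80 (20-40% non-assessable)
- d = extra share assessable on iNO, 0 to 0.15
- g = how far below the others the newly assessable subjects score, 0.5 to 1.0 SD

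Formulas:
- Bias = -[d/(a+d)] × g
- Variance of the iNO scores, v = 1 + [d/(a+d)] × [a/(a+d)] × g²
- SE = √(1/(65a) + v/(65(a+d)))
- Type I error = Φ(|bias|/SE - 1.96) + Φ(-|bias|/SE - 1.96)

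Worked case, a = 0.70, d = 0.10, g = 1: bias = -0.10/0.80 = -0.125 SD; v = 1 + 0.125 × 0.875 = 1.109; SE = √(1/45.5 + 1.109/52) = 0.208; type I error = 9.2%.

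| d | Bias (SD) | Type I error |
|---|---|---|
| 0 | 0 | 5.0% |
| 5 points | -0.03 to -0.08 | 5.3% to 6.3% |
| 10 points | -0.06 to -0.14 | 6.0% to 9.8% |
| 15 points | -0.08 to -0.20 | 7.0% to 14.7% |

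The sign reverses if iNO makes fewer subjects assessable.

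**Loss of information alone.** With equal exclusion, power for a 0.5 SD effect falls from 81% (65 per arm) to 72% with 20% lost (52 per arm) and 60% with 40% lost (39 per arm).

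**Whether ranking everyone cures it.** Take an assumed case with no neurologic effect and no deaths. On placebo, 75% are examined and score high, and 25% are never assessable. On iNO, 75% score high, 10% become assessable and score low, and 15% are never assessable. The win difference is P(iNO better) - P(placebo better), and its true value is 0.
- Exclusion as planned: a share 0.10/0.85 of examined iNO subjects score low, so the difference is -0.118.
- All subjects, never-assessable ranked lowest: iNO better 0.75 × 0.25 + 0.10 × 0.25 = 0.2125; placebo better 0.75 × (0.10 + 0.15) = 0.1875; difference +0.025.
- All subjects, never-assessable tied with the median examined score (here the high score): placebo better 0.10, iNO better 0; difference -0.10.

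Neither convention returns 0, and their signs differ. A single ranking would exchange one dependence on assessability for another. Showing two makes the dependence visible.

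**The case against.** Several stronger readings are tempting, and the documents do not support them.

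A reader might infer that the sickest patients do leave the comparison unequally. No exclusion rate is given, overall or by arm, and with equal loss of like subjects the bias is zero. Blinding of participants and investigator also removes one route, a pause decided with knowledge of the allocation. It does not remove a drug effect on the patient's condition.

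A reader might infer that iNO acts on assessability through oxygenation. Section 2.3.3 reports better oxygenation in a meta-analysis within its review of iNO safety, which it places mainly in ARDS. Nothing in the documents ties oxygenation to permission to pause sedation, and the drug is off before days 2 and 3. The route is an inference and is weaker after day 1. An effect on heart or brain injury, which is the trial's hypothesis, would raise the same question without ongoing dosing.

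A reader might see a flat contradiction with the asterisk. A milder reading is open: FOUR is recorded in everyone and analysed only when the patient was off sedation. The text does not say so, so the passages still need reconciling.

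A reader might take the rule to drop whole subjects. It can equally be applied assessment by assessment, with the mixed models of section 2.5.2 using a subject's other days. That softens the loss but does not help a subject who is never assessable, or missingness that depends on the unrecorded state.

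Finally, this is one of many secondary endpoints. CPC, mRS, NSE, EEG and awakening time also bear on brain injury and do not carry this exclusion. That limits the consequence, but section 2.5.3 still lets an improvement in any one secondary clinical outcome count as preliminary evidence.

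**Conclusion.** The concern holds as a risk. The plan states a rule that selects FOUR assessments by a post-randomisation condition, and its missing-data provisions neither address that selection nor would reveal it. The likely distortion is modest: a 10-point difference in assessability moves the comparison by about a tenth of an SD and can come near to doubling the nominal 5% error rate at the upper end. Those figures rest wholly on the assumed exclusion rates, score gap and normal approximation. The direction cannot be known in advance. The consequence is confined to what may be concluded from FOUR, so the point deserves a change to the plan but does not threaten the trial's main result.

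**What to change.** 1. Keep the off-sedation Motor + Brainstem score as the descriptive neurologic measure, and state whether the exclusion applies to the assessment or to the subject.
2. Beside it, prespecify a rank test on all randomised subjects, with deaths before any examination lowest and never-assessable subjects next. Repeat it with never-assessable subjects tied with the median examined score. Name in advance which daily score enters the ranking. The last assessable one is safer than the best of three, which tends to rise with the number of examinations permitted.
3. Report non-assessable counts and reasons by arm and day.
4. Draw no efficacy inference from FOUR unless the off-sedation and all-randomised analyses agree.
5. Reconcile the asterisk with the exclusion: say either that FOUR is recorded in all subjects or that it is not expected in all.

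The plan already uses such a convention in section 2.4, where awakening times beyond 96 h are set to 100.

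The cost is SAP text, a small change to the endpoint wording in section 2.4 and the Synopsis (with the IRB approval that section 4 requires), and one data item. Section 2.2 records sedation and neuromuscular blockade but lists no field for a pause that was not permitted or why. The statistical downside is that the rank given to never-assessable subjects is a convention, and the rank analysis mixes assessability with neurologic status. That is why it should stand beside the off-sedation analysis and not replace it. No change in patient care is involved.
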